6.1 Full Analysis Set

The Full Analysis Set (FAS) consists of all randomized subjects. This analysis set will be used for sensitivity analyses of efficacy endpoints and will be analyzed according to randomized treatment group.

6.2 Safety Analysis Set

The Safety Analysis Set (SAS) consists of all randomized subjects who received at least 1 dose of IP post-randomization. This analysis set will be used for analyses of the safety endpoints during the Post-randomization Period according to actual treatment received.

6.3 PK Analysis Sets

PK Concentration Analysis Set

The PK Concentration Analysis Set which will include all randomized subjects who received at least 1 dose of IP post-randomization and have at least 1 reported serum concentration of ABP 501 or Humira on or after the day of randomization. This analysis set will be used for analyses of PK concentrations during the Post- randomization Period according to actual treatment received.

PK Parameter Analysis Set

The PK Parameter Analysis Set consists of all randomized subjects who receive at least one dose post-randomization and who have an evaluable ABP 501 or Humira serum concentration-time profile between weeks 28 and 30. This analysis set will be used for the primary analysis of the primary and secondary PK endpoints and will be analyzed according to actual treatment received.

Per-protocol PK Parameter Analysis Set

The Per-protocol PK Parameter Analysis Set consists of all subjects in the PK Parameter Set who do not have an important protocol deviation during the study that could affect the primary PK endpoints. This analysis set will be used for a sensitivity analysis of the primary PK endpoints and will be analyzed according to actual treatment received.

6.4 Health-related Quality-of-Life or Health Economics Analyses Set(s)

None.

Protocol Number: 20200497

Date: 10FEB2023 Page 21 of 36

6.5 Per-protocol Efficacy Analyses Set

The Per-protocol Efficacy Analysis Set consists of all subjects who are randomized and receive all assigned doses post-randomization and who have not experienced an important protocol deviation that may affect the evaluation of the efficacy endpoints. This analysis set will be used for primary analysis of the secondary efficacy endpoints and will be analyzed according to actual treatment received.

6.6 Interim Analyses Set(s)

None.

6.7 Study-specific Analysis Set

Lead in Treated Set

The Lead in Treated Set (LTS) consists of all enrolled subjects treated with at least 1 dose of IP during the Lead-in Period. This analysis set will be used for all analyses for the Lead-in Period and will be analyzed according to actual treatment received.

7. Planned Analyses

7.1 Interim Analysis and Early Stopping Guidelines

None.

7.2 Primary Analysis

None.

7.3 Final Analysis

The final analysis for the study will be performed after all subjects reach Week 32 or terminate early.

8. Data Screening and Acceptance

8.1 General Principles

The objective of the data screening is to assess the quantity, quality, and statistical characteristics of the data relative to the requirements of the planned analyses.

Data screening process will be documented in a data management plan by Parexel and agreed by Amgen. In addition to the data screening built into the Parexel Data Management Plan, the programming of analysis datasets, tables, figures and listings (TFL) provides additional data screening.

When the database has been declared to be complete and accurate, the database will be locked. Database lock will follow the standard operating procedure(s) at Parexel.

Protocol Number: 20200497

Date: 10FEB2023 Page 22 of 36

8.2 Data Handling and Electronic Transfer of Data

Clinical data will be entered in RAVE database and exported as SAS® version 9.4 or higher datasets. Converted datasets will be created using SAS® and following standard Clinical Data Interchange Standards Consortium Standard Data Tabulation Model (CDISC SDTM, version 1.4, Implementation Guide version v3.2) conventions. Analysis datasets will be created using SAS® and following CDISC Analysis Data Model (ADaM, version 2.1, Implementation Guide 1.1) standards.

Medical history and AEs will be coded using the current version of Medical Dictionary for Regulatory Activities (MedDRA) at the time of the final analysis to assign a system organ class (SOC) and preferred term (PT) to each event. Adverse events and abnormal laboratory results considered as AEs are assigned a toxicity grade according to National Cancer Institute (NCI-US) Common Terminology Criteria for Adverse Events (CTCAE) version 4.03. Prior and concomitant medications will be coded using the current version of the World Health Organization Drug Dictionary (WHO-DD) at the time of the final analysis.

8.3 Handling of Missing, Below LLOQ and Incomplete Data

Missing PK concentration data and endpoints will not be imputed.

For the purpose of calculating AUC $_{tau}$, concentrations that are below the LLOQ after t_{max} will be excluded; values less than the LLOQ that are encountered prior to t_{max} will be set to zero and included. Individual AUC $_{tau}$ will be flagged if less than 2 post t_{max} concentration values are reported or less than 2 post t_{max} concentration values are above LLOQ.

For summary statistics and linear plots for the PK concentrations, concentration values < LLOQ will be set to zero. For log-linear plots, concentration values below LLOQ will not be displayed.

The handling of missing values for efficacy endpoints are detailed in Section 9.6.

Missing safety and ADA endpoints will not be imputed.

Imputation for Partial or Missing Dates

If dates are missing or incomplete for an AE (including deaths) or concomitant medication, the following algorithm will be used for imputation:

Stop Date	
	Stop Date

Protocol Number: 20200497

Date: 10FEB2023 Page 23 of 36

		Complete: yyyymmdd		Partial: yyyymm		Partial: yyyy		Missin g
		<1st dose	≥1st dose	<1st dose yyyym m	≥1st dose yyyymm	<1st dose yyyy	≥1st dose yyyy	
Partial: yyyym m	= 1st dose yyyymm	2	1	n/a	1	n/a	1	1
	≠ 1st dose yyyymm		2	2	2	2	2	2
Partial: yyyy	= 1st dose yyyy	- 3	1	3	1	n/a	1	1
	≠ 1st dose yyyy		3	Č	3	3	3	3
Missing		4	1	4	1	4	1	1

- 1 = Impute as the date of first dose
- 2 = Impute as the first of the month
- 3 = Impute as January 1 of the year
- 4 = Impute as January 1 of the stop year

Note: If the start date imputation leads to a start date that is after the stop date, then there is a data error and do not impute the start date.

Imputation rules for partial or missing stop dates:

- 1. Initial imputation
 - a. For partial stop date "mmyyyy", impute the last of the month.
 - b. For partial stop date "yyyy", impute December 31 of the year.
 - c. For completely missing stop date, do not impute.
- 2. If the stop date imputation leads to a stop date that is after the death date, then impute the stop date as the death date.
- 3. If the stop date imputation leads to a stop date that is before the start date, then there is a data error and do not impute the stop date.

Imputation rules for partial or missing death dates:

- 1. If death year and month are available but day is missing:
 - a. If "mmyyyy" for last contact date = "mmyyyy" for death date, set death date to the day after the last contact date.
 - b. If "mmyyyy" for last contact date < "mmyyyy" for death date, set death date to the first day of the death month.
 - c. If "mmyyyy" for last contact date > "mmyyyy" for death date, data error and do not impute.
- 2. If both month and day are missing for death date or a death date is totally missing, set death date to the day after the last contact date.

Protocol Number: 20200497

Date: 10FEB2023 Page 24 of 36

The imputed dates will be used to assess whether AEs should be considered as treatment-emergent and if medications should be included in the safety summaries as prior or concomitant, however the original, partial dates will be included in data listings.

8.4 Detection of Bias

None.

8.5 Outliers

Individual ABP 501 and Humira serum concentration-time points, if considered anomalous, may be excluded from the analysis. If a subject has a protocol deviation that is thought to potentially affect serum concentration assessment, the pharmacokineticist may decide to exclude the value following a review of the available documentation (bioanalytical report, clinical report, etc). Any such exclusion will be documented and clearly outlined in the clinical study report (CSR).

Entire individual PK profile for a subject may be excluded following review of the available documentation. Any such exclusion will be clearly listed in the CSR along with justification for exclusion.

8.6 Distributional Characteristics

None.

8.7 Validation of Statistical Analyses

All report outputs will be produced/all statistical analyses will be performed using SAS® version 9.4 or a higher version in a secure and validated environment.

Programs will be developed and maintained and output will be verified in accordance with current standard operating procedures at Parexel. The validation process is repeated any time TFLs are re-delivered with different data. Execution of this validation process is documented throughout the study. The entire set of TFLs will be checked for completeness, accuracy prior to its delivery to Amgen.

9. Statistical Methods of Analysis

9.1 General Considerations

All statistical analyses will be performed using SAS® (Version 9.4 or higher).

Unless otherwise specified, descriptive data summaries will be tabulated by treatment for all endpoints. Categorical data will be summarized using number of subjects, frequency and percentages of subjects falling into each category, with the denominator

Protocol Number: 20200497

Date: 10FEB2023 Page 25 of 36

for percentages being the number of subjects in the analysis sets for each treatment group, unless otherwise noted. Percentages will be rounded to one decimal place except for 100%, which will have no decimal place.

All continuous variables will be summarized using mean, standard deviation, median, minimum, maximum, 25th percentile (Q1), 75th percentile (Q3), and number of subjects with observations. The mean, geometric mean, median, Q1, and Q3 will be presented to one decimal place greater than the original data, standard deviation will be two decimal places greater than the original data, and the minimum and maximum will have the same number of decimal places as the original data.

For PK endpoints, additional precision rules are as follow:

Pharmacokinetic serum concentrations will be reported in ng/ml with 3 decimal places and will follow the general conventions for summary statistics.

Pharmacokinetic parameters with units of ng/ml or h*ng/ml will be converted to ug/ml or h*ug/ml with 1 decimal place.

Summary Statistics	Reporting Precision			
CV%/geometric CV%	1 d.p.			
Geometric LS mean	2 d.p.			
Geometric LS mean ratios	4 d.p.			
CI	Same number of decimal places as the associated statistic			

d.p.= decimal place(s)

Confidence intervals may also be provided (when specified).

For any of the summaries that are to be done by visit, the derived analysis study visit as defined in Section 5.1 will be used for analysis unless otherwise noted.

9.2 Subject Accountability

The following information will be summarized for subject disposition and accountability for each of the analysis sets defined in Section 6, unless stated otherwise:

- Number of subjects enrolled in the Lead-in Period will be summarized by region, country, and site using LTS. Similarly, number of subjects randomized will be summarized by region, country, and site using the FAS.
- Subject disposition summary will include

Protocol Number: 20200497

Date: 10FEB2023 Page 26 of 36

Number of subjects in the LTS who discontinued treatment with reason of discontinuation, discontinued treatment with reason of discontinuation related to COVID-19, completed the Lead-in Period and who failed the Lead-in Period (i.e., lead-in failures) with reason for lead-in failures for the Lead-in Period and reason for lead-in failures related to COVID-19 for the Lead-in Period;

- Number of subjects who were randomized, who were treated with IP postrandomization, completed treatment, discontinued treatment with reason of discontinuation, discontinued treatment with reason of discontinuation related to COVID-19, completed study, and discontinued study with reason of discontinuation and discontinued study with reason related to COVID-19 for the Post-randomization Period
- Summary of analysis sets with reasons for exclusion from each analysis set (for all screened subjects)
- Randomization list for the FAS
- List of discontinued subjects from IP and/or study using the LTS for the Lead-in
 Period and using the FAS for the Post-randomization Period

9.3 Important Protocol Deviations and COVID-19 Related Protocol Deviations

Important Protocol Deviations (IPDs) data will be identified and recorded. The study team will conduct on-going reviews of the IPD data throughout the study and the resulting set of subjects to be included in the Per-protocol PK Parameter and Per-protocol Efficacy analysis sets. The Per-protocol analysis sets must be finalized prior to database lock of the final analysis.

For the Post-randomization Period, a summary of incidence of IPDs will be based on FAS and tabulated using number and percentage of subjects by deviation type (including COVID-19 related) and randomized treatment group. A listing of subjects with IPDs will be provided (with a flag indicating whether the deviation leads to exclusion from the Perprotocol PK Parameter or Efficacy analysis sets and a flag indicating whether an IPD is COVID-19 related) based on FAS.

For the Lead-in Period, a summary of incidence of IPDs will be based on LTS and tabulated using number and percentage of subjects by deviation type (including COVID-

Protocol Number: 20200497

Date: 10FEB2023 Page 27 of 36

19 related). A listing of subjects with IPDs (with a flag indicating whether an IPD is COVID-19 related) will be provided based on LTS.

All COVID-19 related Protocol Deviations (PDs) will be summarized by COVID-19 related deviation type for the FAS and LTS. A listing of subjects with COVID-19 related PDs will be provided for the FAS and LTS.

A listing of subjects affected by COVID-19 related study disruptions in the LTS for the Lead-in Period and in the FAS for the Post-randomization Period will also be provided, if applicable. The definition of "COVID-19 related study disruption" will be determined by the Amgen's study team.

9.4 Demographic and Baseline Characteristics

The following demographics and baseline characteristics will be summarized descriptively by treatment group for each of the analysis sets defined in Section 6.

- age (in years, at time of signing informed consent) and age category (<65 vs ≥65),
- race,
- sex.
- ethnicity,
- height,
- weight,
- body mass index (BMI),
- geographic region,
- prior biologic use for psoriasis,
- duration of psoriasis (in years) and duration of psoriasis category,
- BSA affected by psoriasis,
- sPGA,
- baseline PASI score,
- Prior use of systemic or photo therapies.

Medical history will be coded according to MedDRA and unresolved findings will be summarized by SOC and PT for the LTS.

Protocol Number: 20200497

Date: 10FEB2023 Page 28 of 36

9.5 PK Analyses

9.5.1 Analyses of Primary PK Endpoint(s)

9.5.1.1 Primary Analysis

The primary analysis of the primary PK endpoints, AUC_{tau} and C_{max} , between Week 28 and 30 will be performed based on the PK Parameter Analysis Set according to the actual treatment groups (switching group versus continued use group).

The point estimates and 90% CIs for the GMRs between ABP 501 and Humira for AUC_{tau} and C_{max} between Week 28 and 30 will be estimated using an analysis of covariance (ANCOVA) model adjusting for stratification factors, weight and PK trough concentration at the end of the Lead-in Period (week 12). Prior to statistical testing, the PK parameters will be logarithmically transformed (natural log). Point estimates and 90% CIs for the mean difference in logarithmic PK parameters will be estimated using the ANCOVA model, which will then be transformed back to the original scale to obtain the point estimates and 90% CIs for GMR. To establish interchangeability, the 90% CIs of GMR of ABP 501 vs Humira for AUC_{tau} and C_{max} (between Week 28 and 30) from the primary analysis should fall within the prespecified similarity margin (0.8, 1.25).

9.5.1.2 Secondary Analyses

 AUC_{tau} and C_{max} of ABP 501 and Humira between weeks 28 and 30 will be listed by subject and summarized descriptively by treatment group using PK Parameter Analysis Set.

To assess the robustness of the primary analysis result, the ANCOVA analysis described above will be repeated using the Per-protocol PK Parameter Analysis Set. Furthermore, the primary ANCOVA analysis will be repeated by adding gender as a covariate in addition to the covariates specified for the primary analysis (stratification factors, weight and PK trough concentration at the end of the Lead-in Period [Week 12]) using PK Parameter Analysis Set.

9.5.2 Analyses of Secondary PK Endpoints

The analyses of the secondary PK endpoints of t_{max} between Week 28 and 30 and C_{trough} between Week 14 and 28 will be based on the PK Parameter Analysis Set according to the actual treatment groups. t_{max} will be listed by subject and summarized descriptively (only median, min and max) by the treatment group. C_{trough} between Week 12 and 28 will be summarized descriptively by visit and treatment group. For post-randomization C_{trough} assessment (between Week 14 and 28), the point estimates and 90% CIs for GMR for C_{trough} between the two treatment groups will be estimated using an ANCOVA model

Protocol Number: 20200497

Date: 10FEB2023 Page 29 of 36

adjusting for stratification factors, weight and PK trough concentration at the end of the Lead-in Period (Week 12).

In addition, C_{trough} between Week 12 and 28 will be summarized descriptively and presented graphically by box plot by analysis visit and actual treatment group using the PK Concentration Analysis Set.

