8.5 Pharmacokinetics

Serum samples will be collected for measurement of serum concentrations of investigational product as specified in the Schedule of Assessments (Table 1-1). Instructions for the collection, handling, storage and shipment of biological samples will be provided in the Laboratory Manual. Blood samples for PK testing will be collected from all subjects. PK samples for baseline, week 6, week 12, week 16, week 20, and week 28 should be taken prior to administration of investigational product. PK samples for subsequent time points should be collected within the tolerance window specified in Table 1-2.

The actual date and time (24-hour clock time) of each sample will be recorded.

Samples collected for analyses of investigational product serum concentration may also be used to evaluate safety or efficacy aspects that address concerns arising during or after the study.

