9.5.2 Secondary Endpoint(s)

9.5.2.1 Secondary Pharmacokinetic Endpoints

The analyses of the secondary PK endpoints of time of maximum concentration (t_{max}) between weeks 28 and 30 and trough concentration (C_{trough}) between weeks 14 and 28 will be based on the PK Parameter Analysis Set according to the actual treatment groups (switching group versus continued-use group). t_{max} will be summarized descriptively by treatment group and C_{trough} between weeks 14 and 28 will be summarized descriptively by visit and treatment group. The point estimates and 90% CIs for GMR for C_{trough} between the two treatment groups will be estimated using an ANCOVA model adjusting for stratification factors, weight, and PK trough concentration at the end of the lead-in period (week 12).

Mean serum concentration-time data post randomization will be presented graphically using PK Concentration Analysis Set.

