5.2 Pharmacokinetic

Pharmacokinetic parameters will be calculated from the serum concentration-time data using noncompartmental methods (Phoenix WinNonlin®, version 8.2 or higher, Pharsight Corp, St. Louis, MO) and actual sampling times. The following PK parameters will be reported:

Variable	Definition
AUC _{tau}	area under the curve from week 28 over the dosing interval up to week 30 using the observed values.
C_{max}	Maximum observed serum concentration obtained directly from the concentration time profile. If multiple maxima occur at equal concentrations, the first temporal value will be taken.
t _{max}	Time at which the maximum serum concentration was observed obtained directly from the concentration time profile
C_{trough}	trough concentration

The AUC $_{tau}$ is the sum of areas up to the dosing interval and will be calculated using the linear trapezoidal rule. AUC $_{tau}$ will be calculated based on actual time post dose for the observed values between week 28 and 30 without extrapolation or interpolation, and estimated up to the last measurable concentration. Individual AUC $_{tau}$ will be flagged and excluded from summary statistics and statistical testing if less than 2 post t_{max} concentration values are reported or less than 2 post t_{max} concentration values are above LLOQ. t_{trough} at a specific week is defined as the pre-dose level for the respective week.

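### The Ctrough ratio for weeks 14 to 28 is estimated only in subjects who later have an evaluable week 28-30 profile, so valid earlier troughs from other treated subjects never enter a between-group estimate

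*SAP*

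**What the plan says.** SAP 9.5.2 states that the Ctrough analysis "between Week 14 and 28 will be based on the PK Parameter Analysis Set". Protocol 9.5.2.1 has the same rule ("between weeks 14 and 28 will be based on the PK Parameter Analysis Set"). Within it, the GMR "between the two treatment groups will be estimated using an ANCOVA model", with a 90% CI, adjusting for the stratification factors, weight and the week-12 trough.

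SAP 6.3 limits the PK Parameter Analysis Set to randomized subjects with at least one post-randomization dose "who have an evaluable ABP 501 or Humira serum concentration-time profile between weeks 28 and 30". SAP version 2.0 relaxed the dosing condition, which had been all assigned doses, but kept the profile condition.

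Ctrough itself needs no profile. SAP 5.2 says that it "at a specific week is defined as the pre-dose level for the respective week". Protocol 8.5 gives the sampling: "PK samples for baseline, week 6, week 12, week 16, week 20, and week 28 should be taken prior to administration". The post-randomization troughs are thus at weeks 16, 20 and 28.

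The wider PK Concentration Analysis Set is used for Ctrough in SAP 9.5.2 only for output that is "summarized descriptively and presented graphically by box plot by analysis visit and actual treatment group using the PK Concentration Analysis Set". No ratio or interval is planned there. SAP 8.3 does not impute missing PK data.

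**The concern.** A week-16 trough enters the comparison only if the same subject has an evaluable profile some 12 weeks later. That selects on what happens after randomization. Protocol 7.2 lists adverse events and a need for alternative therapy among the reasons for leaving. Either could plausibly follow low exposure or antidrug antibodies after a switch. If so, the subjects removed are those in whom a switching effect on exposure would be seen.

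AUCtau and Cmax cannot be observed in subjects who leave before week 28. For them, the week-16 trough (after the first ABP 501 doses) and the week-20 trough (after the return to adalimumab) are the only post-switch PK data that could support an estimate with an interval. The other planned PK model runs do not fill the gap: the per-protocol repeat, the added gender covariate and the neutralizing-ADA-negative subgroup all keep the same set or narrow it. Efficacy, by contrast, has a sensitivity analysis in the Full Analysis Set by randomized group (SAP 9.6.2.2).

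**Working it through.** **Inputs.** SAP 3.2: 342 randomized 1:1, 15% without evaluable primary PK, CV 53%, true GMR 1, margin 0.8 to 1.25, two one-sided tests at 0.05. Protocol 6.7: half-life about 14 days. The documents state no sample size, CV or margin for Ctrough. The primary-endpoint CV is used below as an assumed stand-in, and all calculations are unadjusted.

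**The plan's own figure.** Log SD = sqrt(ln(1 + 0.53²)) = 0.4976. Evaluable: 342 × 0.85 = 290.7, taken as 145 per arm. Power for one endpoint is 97.0%; for both together it is at least 2 × 0.9696 − 1 = 93.9%. The stated figure of at least 90% is reproduced and is not in question.

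**Subjects outside the Ctrough GMR.** 342 × 0.15 = 51.3, so at most about 51. The 15% covers both withdrawal before week 28 and reaching week 28 without evaluable endpoints. Anyone who leaves before week 16 or week 20 has no trough at that visit to recover. If 25%, 50% or 75% of the 51 had given a particular trough (assumed), about 13, 26 or 38 would be added back.

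**Selection.** Let completers have GMR 1, let r be the leavers' trough relative to completers, and let d be the share leaving. If only switching-arm leavers are low, the all-subject GMR is r^d. If leavers in both arms are equally low, it is r^(d switching − d continued use).

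The table takes 15% leaving per arm, with only switching-arm leavers low. The half-width is for the 90% CI on the log scale with 171 per arm. It uses a switching-arm log variance of 0.2476 + 0.15 × 0.85 × (ln r)², a continued-use variance of 0.2476, and t = 1.649.

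| r (assumed) | All-subject GMR | Planned GMR | Half-width, 171 per arm |
|---|---|---|---|
| 0.8 | 0.967 | 1.00 | 0.089 |
| 0.5 | 0.901 | 1.00 | 0.094 |
| 0.3 | 0.835 | 1.00 | 0.104 |
| 0.2 | 0.786 | 1.00 | 0.115 |

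With 15% leaving in both arms and equally low troughs, the exponent is 0 and the GMR does not move.

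**Precision.** For completers alone, 145 per arm, the half-width is 1.650 × 0.4976 × sqrt(2/145) = 0.096, an interval of 0.908 to 1.101 at GMR 1. If leavers look exactly like completers, 171 per arm gives 0.089, or 0.915 to 1.093. The table shows that this narrowing shrinks as r falls and has reversed by r = 0.3.

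A second scenario has 10% of switching and 5% of continued-use subjects leaving at r = 0.25. The GMR is 0.25^0.05 = 0.933. The variances are 0.2476 + 0.09 × 1.922 = 0.421 and 0.2476 + 0.0475 × 1.922 = 0.339. The half-width is 1.649 × sqrt((0.421 + 0.339)/171) = 0.110, again wider than 0.096.

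**How extreme are these r values?** The week-16 trough comes 28 days after the week-12 trough, which is two half-lives. Receiving no drug in between would leave 0.5² = 0.25 of the week-12 level. An r of 0.25 or less therefore needs clearance well above the stated half-life, or a trough already low at week 12, which the planned covariate partly removes.

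**The case against.** The strongest reply is that nothing is hidden and nothing decisive is affected. Ctrough is secondary, with no margin or decision rule, and interchangeability rests on AUCtau and Cmax alone (SAP 2.2 and 9.5.1.1). Using one set for all PK parameters keeps the same subjects across measures and is the protocol's own choice. The other troughs are summarized and "presented graphically by box plot by analysis visit and actual treatment group" in the wider set. Discontinuations by reason, adverse events leading to discontinuation, and ADA by visit are also reported. Large distortions need extreme troughs, and randomized subjects are week-12 PASI 50 responders.

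Most of this stands, and it limits the size of the point. It does not supply a between-group estimate with an interval for the omitted troughs. The box plots are also a weaker substitute than they look. SAP 5.1 gives the switching and continued-use labels to subjects who receive all assigned treatments, and puts those who deviate from the regimen in separate groups. Read literally, an early leaver may not appear in either main group's box plot.

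The same rule shows that changing the analysis set alone would not be enough. SAP 6.3 analyses the PK Concentration Analysis Set by actual treatment, so early leavers could still fall outside a two-group ratio.

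A reader might also infer that restoring these subjects sharpens the estimate. The working does not support that: the interval narrows if leavers resemble completers, in which case there is little bias to remove, and widens if their troughs are low enough.

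**Conclusion.** The point holds, as a moderate one about a secondary endpoint. The Ctrough GMR is conditional on a later event, without any need in the definition of Ctrough. At most about 51 of 342 subjects are involved, and fewer at weeks 16 and 20. With 15% leaving per arm and low troughs in switching-arm leavers only, the all-subject GMR would be 0.97 to 0.79 for r from 0.8 to 0.2, while the planned GMR reads 1.00. The lower end rests on extreme assumptions, and balanced leaving with equal troughs gives no shift. The shares and r values are illustrations, not document figures.

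Two stronger readings are not supported. One is that the interchangeability conclusion is biased by this choice: Ctrough plays no part in that decision. The other is that 51 subjects' data are discarded at every visit: 51 is a planning ceiling, and the available troughs are still reported descriptively. One uncertainty remains. The SAP does not fully define an evaluable profile, so a subject who stops product but stays for sampling is a grey area. A subject who withdraws before week 28 is clearly excluded.

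**What to change.** In SAP 9.5.2, add a by-visit Ctrough ANCOVA at weeks 16, 20 and 28 with the same covariates, in the PK Concentration Analysis Set. Specify that:

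- It uses every subject with a true pre-dose sample taken while still on product at that visit; samples drawn after product has stopped are not counted as troughs.
- Subjects are grouped by randomized arm, or by treatment received up to that visit, and not by the whole-period actual-treatment label in SAP 5.1.
- One rule applies to troughs below the LLOQ on the log scale, with sensitivity to it shown. The zero that SAP 8.3 uses for summaries has no logarithm.

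Keep the PK Parameter Analysis Set version alongside, and record the change in SAP Section 10. That section already relaxed the same set on the ground that it could shut out evaluable subjects.

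The cost is SAP wording and one more run of an existing model on data already collected. The downside is that the estimate or interval may look slightly less favourable.
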